Cover Page

Study Protocol

Study Title: Unilateral Strength Training and Mirror Therapy for Patients with Chronic

Stroke. A Pilot Randomised Controlled

Trial Document creation date: July 12th 2015

NCT number [not yet assigned].

Identifiers: [NCT ID not yet assigned]

Study Protocol for Unilateral Strength Training and Mirror Therapy for Patients with Chronic Stroke. A Pilot Randomised Controlled Trial ([name], IT Sligo)

The intervention comprised of a home-based isometric strength training programme performed under supervision by two therapists. The participant's less-affected (LA) lower limb was strapped into an ankle brace securing the ankle joint at a 100° angle (10° plantarflexion). Subjects were seated on a chair with back support, with a knee joint angle at 120°. Following a warm-up consisting of unilateral submaximal isometric contractions, the main part of the training programme consisted of 4 sets of 5 maximal effort isometric ankle dorsiflexion contractions, performed with the LA limb only, held for 5 seconds with 5 seconds rest between repetitions and 3 minutes rest between sets. The same protocol was followed 3 times per week for 4-weeks (12 sessions).

The Unilateral Strength Training only (Cross-education) group exercised without a mirror; the Experimental Group (Mirror Therapy) group observed the reflection of the LA lower limb in the mirror while training. Prompts to focus on the reflection in the mirror were given to the Mirror Strength Training group only; other verbal cues were identical for all participants of both groups.

Cover Page

Statistical Analysis Plan

Study Title: Unilateral Strength Training and Mirror Therapy for Patients with Chronic

Stroke: A Pilot Randomised Controlled

Trial Document creation date: July 12th 2015

NCT number [not yet assigned].

Identifiers: [NCT ID not yet assigned]

Statistical Analysis Plan for Unilateral Strength Training and Mirror Therapy for Patients with Chronic Stroke: A Pilot Randomised Controlled Trial ([name], IT Sligo)

Data was analysed using IBM SPSS for Windows (Version 20, Chicago, IL, USA). All variables were tested for normal distribution using the Shapiro-Wilk test. Sample demographics and outcome measures are described in Mean±SD. Between group differences for demographic characteristics were tested for using the Independent t test, the Mann-Whiteny U test and the Chi Square test. Within group means (T1 v T2 and T1 v T3) were analysed using the Paired-Samples-t-test for normally distributed data and the Wilcoxon Signed Rank test for non-normally distributed data. Between group differences (ST v MST) in change over the intervention were tested for using the independent-sample-t-test (normal distribution) and the Mann-Whitney U test (non-normal distribution or non-continuous scale). A *p*-value <0.05 was considered statistically significant and effect sizes expressed as either Cohen's d or *r*. Effect size for within group differences were calculated as follows:

Paired differences effect size = $\frac{mean}{Sd}$ or $r=Z/\sqrt{n}$. Effect sizes for between group differences for the independent-samples-t-test were calculated using and expressed as Cohen's d. For the Mann-Whitney U test, between group differences were calculated as $r=Z/\sqrt{n}$.

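### An unspecified Shapiro-Wilk check chooses the test and the effect-size scale, so one outcome can be reported on non-comparable scales across arms and time intervals

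*SAP*

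**What the plan says.** The SAP is one unnumbered section. On normality it says only "All variables were tested for normal distribution using the Shapiro-Wilk test". It does not state which values are checked, whether arms are separate or pooled, or what cut-off applies to the check.

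The within-group rule reads "Within group means (T1 v T2 and T1 v T3) were analysed using the Paired-Samples-t-test" if normality is accepted; if it is not, the Wilcoxon test takes its place. The significance level is 0.05, and each effect size is given as Cohen's d or as r. The SAP then says "Effect size for within group differences were calculated as follows" and offers two formulas: mean over SD for paired differences, or Z over the square root of n. It is not said whether n counts pairs or observations.

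For the randomised comparison, "Between group differences (ST v MST) in change over the intervention were tested for using the independent-sample-t-test" if normal, and otherwise "the Mann-Whitney U test (non-normal distribution or non-continuous scale"). The provision for non-continuous scales appears here and not in the within-group rule.

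Nothing requires the same test or the same effect-size scale for one outcome in both arms or both intervals. The protocol describes the training programme and the two groups. It lists no outcomes, gives no sample size and has no statistical text that fills the gap.

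**The concern.** One unspecified step settles both the p-value method and the scale of the effect size. Read literally, the check covers raw scores, but the paired t-test's assumption concerns the paired differences. Two analysts could each follow the text on the same data and report different tests. If the check is run per arm, ST may be reported as mean/SD and MST as r for the same outcome. If the arms are pooled, T1 v T2 and T1 v T3 can still part ways.

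An ordinal outcome that happens to pass Shapiro-Wilk would go to a paired t-test within arms and to Mann-Whitney between arms. The ST v MST test depends on the same check, so the choice of test for the randomised comparison is also not reproducible from the text. In a pilot, effect sizes are a main product, so their comparability matters.

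**Working it through.** The plan contains no figure of its own to reproduce. The check asks how often the open choices change the method, and by how much the scales differ.

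**Inputs.** From the SAP: two arms, two intervals, the test branches, the effect-size formulas and the 0.05 level. Assumed, because the documents do not give them: 10, 15 or 20 patients per arm; Shapiro-Wilk cut-off 0.05; correlation between time points 0.5 to 0.9; distribution shapes. Under the raw-score reading, Wilcoxon is taken if either time point of the pair rejects. Routing simulations used 4,000 trials per cell.

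**1. Normal data, T1 v T2 unless stated.** The closed forms treat the individual checks as independent.
- Differences per arm, arms mismatched: 2 × 0.05 × 0.95 = 9.5%. Simulated 8.7–10.0%.
- Raw scores per arm: rejection in one arm 1 − 0.95² = 9.75%; mismatch 2 × 0.0975 × 0.9025 = 17.6%. Simulated 15.0–18.0%.
- Arms pooled: arm mismatch 0% by construction. The two intervals still differ in 8.5–9.8% (differences) or 5.3–9.3% (raw).
- Differences per arm, the four within-group tests not all alike: 1 − 0.95⁴ − 0.05⁴ = 18.5%. Simulated 17.2–19.0%.
- Two analysts who both pool, one checking differences and one raw scores: 0.05 × 0.9025 + 0.95 × 0.0975 = 13.8%. Simulated 12.3–14.2%.

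**2. Skewed change, differences checked per arm, correlation 0.8: arm mismatch.**

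| Shape of change | n = 10 | n = 15 | n = 20 |
|---|---|---|---|
| chi-square(16) | 16.4% | 21.9% | 27.2% |
| chi-square(8) | 23.8% | 33.2% | 40.8% |
| chi-square(4) | 37.9% | 48.4% | 50.6% |

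A repeat run gave 36–50% for chi-square(4). If both arms reject with the same probability p, mismatch is 2p(1 − p), which is at most 50% (at p = 0.5), so the excess in the last cell is simulation noise. With unequal p the limit does not hold: normal change in one arm and chi-square(1) in the other gives about 71/88/93%.

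**3. Scales.** A true standardised change of 0.8 reads as median mean/SD 0.82–0.83, as r = 0.66 if n counts pairs, and as 0.66/√2 = 0.47 if n counts observations. With n as pairs, the largest possible r is √[1.5(n + 1)/(2n + 1)]: √(16.5/21) = 0.89 at n = 10 and √(31.5/41) = 0.88 at n = 20. Mean/SD has no such ceiling.

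**4. ST v MST routing.** Take Mann-Whitney if either arm rejects. For normal data, gating on change rejects with probability 1 − 0.95² = 9.75%, and gating on raw scores at two time points with 1 − 0.95⁴ = 18.5%. They disagree in 0.0975 × 0.815 + 0.185 × 0.9025 = 24.6% if independent; simulated 23–25%. With chi-square(4) change, disagreement is 44–64%. Type I error of the test gated on change was 4.9–5.3% (normal) and 5.4–5.8% (chi-square(4)), from 10,000 trials per cell.

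**5. ANCOVA against the change-score t-test.** With equal variances, the ratio of error variances is (1 − ρ²)/[2(1 − ρ)] = (1 + ρ)/2, or 0.75, 0.90 and 0.95 at ρ = 0.5, 0.8 and 0.9. Simulated power gains for an arm difference of 1 SD of change, at n = 10/15/20: +10.1/+9.6/+6.4, +1.8/+3.1/+2.1 and +0.3/+0.4/+0.7 points. With chi-square(4) change at ρ = 0.8, the gated test has 64.6/82.3/92.6% and ANCOVA 57.1/74.4/85.5%, a loss of 7.5/7.9/7.1 points.

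**The case against.** The strongest reply is that the SAP has a natural reading. Its within-group effect size is labelled as one for paired differences, which suggests that differences are checked, and pooling the arms would be odd for a within-group analysis. That has force. But differences checked per arm is exactly the reading that gives 9.5% arm mismatch under perfect normality and far more under skew.

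Second, the SAP plans no comparison of within-group effect sizes between arms, because ST v MST has its own test and effect size. This stands and limits the harm to reporting and reproducibility. Third, every percentage rests on assumed sample sizes, correlations and shapes. This also stands: the figures illustrate and do not predict.

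A smaller remedy would state only the values checked, the cut-off and one decision per outcome. That would make the plan reproducible but leave the test and the effect-size scale to depend on a small-sample check.

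Four stronger or wider readings are not supported:
- A reader might infer that the switching inflates false positives in the randomised comparison. The simulated rates stay near 5%; even taking the smaller p-value of the two candidate tests gave 4.5–6.8%.
- A reader might infer that ST v MST escapes because the SAP names change. That names what is tested, not what was checked for normality.
- A reader might take 50% as a general ceiling on mismatch. It needs equal rejection probability in both arms.
- A reader might infer that tests were picked to suit the results. Nothing in the documents shows this.

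**Conclusion.** The point holds and is minor. The SAP leaves open what is checked, in whom, and whether one decision governs an outcome, and that decision sets both the test and the effect-size scale. If differences are checked per arm with 10 to 20 patients each, the arms part ways in about 9–10% of trials with normal change and 36–50% with chi-square(4) change, the latter with the same shape in both arms. The same underlying effect can appear as about 0.8, 0.66 or 0.47 depending on the branch and on the meaning of n. The choice of the ST v MST test is equally undefined, without material damage to its type I error. Sample size, correlation and shape are all assumptions; the omission itself is read directly from the text.

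**What to change.** 1. **Within groups.** List the outcomes and, before analysis, fix by scale type one test and one effect-size scale per outcome, used in both arms and for both T1 v T2 and T1 v T3. For continuous outcomes, report mean paired change with 95% CI and mean/SD of the differences, with the paired t-test. For ordinal or other non-continuous outcomes, use Wilcoxon with r, n being the number of pairs. Name in advance, with the reason, any continuous outcome to be treated as skewed. Keep Shapiro-Wilk as description only.

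2. **ST v MST.** Drop the same gate. For continuous outcomes, use ANCOVA of the T2 value adjusted for T1, with adjusted mean difference and 95% CI and a pre-named rank-based sensitivity analysis. For non-continuous or pre-named skewed outcomes, use Mann-Whitney on change. This takes T2 as the end of the intervention, which the SAP does not define and should state.

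**Cost.** No new data are needed, but the outcomes must be listed and classified. Within groups, always using the paired t-test changes power by at most 0.2 points for normal change and by about −4 to +7 points for chi-square(4) change. The latter is not size-adjusted: type I error there was 7.1–7.6% for paired t and 7.4–8.8% for the gated choice.

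Between groups, ANCOVA gains about 7–10 points at correlation 0.5 (6.4 in the lowest cell) and 1–3 at 0.8, and is neutral at 0.9. It gives up about 7–9 points against the gated test if change is strongly skewed and this was not foreseen. Naming Mann-Whitney in advance stays within 1.4 points of the gated test under that skew, but loses 2–5 points to the t-test if change proves normal. If the data have already been analysed, apply the rule to every outcome and label it as set afterwards.

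### The only between-group outcome analysis is an unadjusted test on change; it is valid, but for t-test outcomes an ANCOVA on the T1 value would be a cheap gain in precision when the T1 slope is clearly below 1

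*SAP*

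**What the plan says.** The SAP is a single unnumbered section. Its between-group outcome analysis reads "Between group differences (ST v MST) in change over the intervention were tested for using the independent-sample-t-test (normal distribution"), and the other branch is "the Mann-Whitney U test (non-normal distribution or non-continuous scale"). I read change over the intervention as T2 minus T1; the time points are not defined further.

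The remaining outcome tests are within arm: "Within group means (T1 v T2 and T1 v T3) were analysed using the Paired-Samples-t-test for normally distributed data", with a signed-rank alternative. The other between-group tests concern demographics: "Between group differences for demographic characteristics were tested for using the Independent t test" and its non-parametric and categorical counterparts. No adjustment follows from them.

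Effect sizes follow the branch. For the t-test, "Effect sizes for between group differences for the independent-samples-t-test were calculated using and expressed as Cohen's d" (the formula is missing from the extracted text); for Mann-Whitney, r = Z/√n. On routing, the SAP says only "All variables were tested for normal distribution using the Shapiro-Wilk test".

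Neither document mentions ANCOVA, regression or any other baseline adjustment. Neither states a sample size, outcome SD, T1–T2 correlation or allocation method.

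**The concern.** T1 is the reference for both within-group comparisons, so a T1 value exists for every outcome and adjustment would need no new data. Subtracting T1 amounts to regressing T2 on T1 with the slope forced to 1. The actual slope is ρ × SD(T2)/SD(T1). If that is clearly below 1, the subtraction over-corrects: the arm that happened to start lower shows a larger apparent gain, whatever the mirror does.

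Both titles call the trial a pilot, so the arms may be small and sizeable chance differences at T1 common. Two things are then at stake: some power, and the reading of the ST v MST difference and its Cohen's d, part of which would reflect the starting values.

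**Working it through.** **Inputs.** From the SAP: unadjusted tests on change, significance at 0.05, and Cohen's d for the t-test branch. Assumed, because the documents are silent: a two-sided test, normal data, 10 or 15 per arm, no stratification on T1, ρ of 0.5 to 0.9, k = SD(T2)/SD(T1) of 1.0 or 1.2, and d on the SD of change. The plan has no figure of its own to reproduce.

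**1. Validity.** In simulated normal trials with no effect, overall type I error was 4.8% to 5.2% for both the change-score t-test and ANCOVA.

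**2. Precision.** In units of SD(T1), change has variance 1 + k² − 2ρk and the ANCOVA residual has variance k²(1 − ρ²). With n per arm, estimating the slope multiplies the ANCOVA variance by 1 + 1/(2n − 4). So

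ratio = k²(1 − ρ²)(1 + 1/(2n − 4)) / (1 + k² − 2ρk).

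Example, n = 15, k = 1, ρ = 0.5: 0.75 × (1 + 1/26) / 1 = 0.78. Example, n = 15, k = 1.2, ρ = 0.7: 1.44 × 0.51 × 1.0385 / 0.76 = 1.00.

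| ANCOVA/change variance | ρ 0.5 | 0.7 | 0.8 | 0.9 |
|---|---|---|---|---|
| k = 1, n = 15 | 0.78 | 0.88 | 0.94 | 0.99 |
| k = 1, n = 10 | 0.80 | 0.90 | 0.96 | 1.01 |
| k = 1.2, n = 15 | 0.90 | 1.00 | 1.04 | 1.01 |
| k = 1.2, n = 10 | 0.93 | 1.03 | 1.06 | 1.04 |

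Simulation agreed closely. With a falling SD (k = 0.8) the ratio is 0.59 to 0.68, but nothing in the documents supports or excludes that case.

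**3. Power.** For an effect of 1 SD of change with k = 1 and ρ 0.5/0.7/0.8/0.9, simulated power moves from about 75% with the change-score test to 85%/80%/78%/76% with ANCOVA at 15 per arm, and from about 56% to 66%/60%/58%/56% at 10 per arm.

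**4. Shift from a T1 gap.** The expected shift is (ρk − 1) × D, where D is the T1 difference in SD(T1) units; dividing by √(1 + k² − 2ρk) gives the shift in d. D has standard error √(2/n), which is 0.447 at 10 per arm and 0.365 at 15. A gap above 0.5 in either direction therefore occurs in 26% and 17% of trials.

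| Shift for D = 0.5 | ρ 0.5 | 0.7 | 0.8 | 0.9 |
|---|---|---|---|---|
| k = 1, difference | −0.25 | −0.15 | −0.10 | −0.05 |
| k = 1, Cohen's d | −0.25 | −0.19 | −0.16 | −0.11 |
| k = 1.2, difference | −0.20 | −0.08 | −0.02 | +0.04 |

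The last row uses slopes of 0.60, 0.84, 0.96 and 1.08.

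**5. Type I error among trials with a gap above 0.5 SD, 15 per arm.** For the change-score test with k = 1 it is about 11.5% at ρ 0.5, 9% at 0.7, just under 8% at 0.8 and 6% to 7% at 0.9, against about 5% for ANCOVA. In the other 83% of trials it is 3.7% to 4.8%, which is why the overall rate stays near 5%. With k = 1.2 it is 8.7% at ρ 0.5 and between 5% and 6% from 0.7 up.

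**The case against.** The strongest reply is that nothing here is wrong. The SAP states what is compared and uses a standard, valid test. The benefit of ANCOVA depends on a slope clearly below 1, which the documents neither support nor exclude. A rising SD is as open as an equal one; at k = 1.2 the precision gain is gone from ρ = 0.7 up, and the conditional error nearly so. In very small arms ANCOVA can lose: at 6 per arm, k = 1.2, ρ = 0.8, simulated power falls from 35% to about 32%. All of this stands. It limits the point to an efficiency improvement of unknown size.

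Three stronger readings are tempting, and the documents do not support them.

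- A reader might infer from step 5 that the planned test inflates type I error. It does not: those rates condition on a large T1 gap, and over all randomisations the rate is about 5%.
- A reader might infer that Mann-Whitney should likewise give way to rank ANCOVA. That would replace a comparison of change with one of T1-adjusted T2 ranks, and in simulated skewed data at ρ = 0.9 it lost up to about 10 power points. It is a trade-off, not a correction.
- A reader might infer from the SAP's past tense that the outcomes had already been analysed. The tense alone does not show whether data had been seen.

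The routing objection also has force. The SAP does not say on which quantity normality is tested, and ANCOVA's assumption concerns residuals, so these need their own check.

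**Conclusion.** The point holds as a modest, low-cost improvement for the t-test branch. The SAP never uses T1 as a covariate in its only between-group outcome analysis, and where the slope is clearly below 1 this costs precision and lets chance T1 imbalance move the reported difference and Cohen's d.

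Under the assumptions above, at 15 per arm with equal SDs, ANCOVA removes 22% of the variance at ρ = 0.5 (1 − 0.78), 12% at 0.7 and about 1% at 0.9. With a slope near 1 there is nothing to gain. The size in this trial cannot be determined without N, SDs and correlations, and allocation stratified on T1 would make large gaps rarer. The figures for d also depend on its denominator; another SD would change their size but not their direction. The shift in d concerns the t-test branch only, since the Mann-Whitney branch reports r.

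**What to change.** For each outcome the SAP sends to the t-test, make the main ST v MST analysis an ANCOVA of the T2 value on group, with that outcome's T1 value as covariate. Check the residuals. Report the adjusted mean difference with its 95% CI, and Cohen's d as that difference divided by the same SD that the planned d uses, so that the scale does not change.

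Keep the change-score t-test as a labelled sensitivity analysis that does not decide the conclusion. Leave the Mann-Whitney branch and its r = Z/√n as planned; a rank ANCOVA there is optional and supportive only. If outcome data had already been examined when this change is made, label the ANCOVA as post hoc.

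The cost is SAP wording, one extra supportive test per t-test outcome and one residual degree of freedom. No new data are needed. If the slope turns out to be near 1, the price is about 2 to 3 power points in small arms: for example 56% to about 54% at 10 per arm, or 35% to 32% at 6 per arm, both with k = 1.2 and ρ = 0.8.

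### For outcomes analysed by t-test, the SAP's mean/Sd and Cohen's d show no small-sample correction; on average they overstate the effect by about 9–4% within arms and 4–2% between arms if arms hold 10–20

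*SAP*

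**What the plan says.** The effect-size definitions stand at the end of the SAP's single unnumbered section.

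- **Within group.** "Effect size for within group differences were calculated as follows": "Paired differences effect size" equals mean over Sd where the paired t-test is used, or r = Z/√n where the Wilcoxon test is used. The mean/Sd formula is legible and has no correction factor.
- **Between group, t-test.** The effect sizes "were calculated using and expressed as Cohen's d". The words after *using*, probably a formula, are not in the text available here. This is a limit of the reading, not a gap in the plan.
- **Between group, rank test.** "For the Mann-Whitney U test, between group differences were calculated as" r = Z/√n.

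The readable text mentions neither Hedges' g nor any other small-sample correction. Both documents call the trial a pilot ("A Pilot Randomised Controlled" in the Protocol title). Neither gives a sample size, allocation ratio, power or target effect, and neither says what the effect sizes will be used for.

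**The concern.** Under normality, the expected value of a sample mean divided by a sample SD is the true standardised effect multiplied by 1/J(df), where J is below 1 and falls as the degrees of freedom fall. The average error is therefore away from zero, its size is known once n is known, and it can be removed by one multiplication. It arises whichever SD is the standardiser, so it is separate from the question of which SD to divide by.

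Two things are at stake, both modest. First, the reported magnitudes are somewhat too large on average, and in a trial labelled a pilot a reader may give those magnitudes weight. Second, the within-arm ratio rests on about half the degrees of freedom of the between-arm one, so it is inflated about twice as much. A reader who sets the before–after effects beside the randomised ST v MST effect is comparing figures inflated by different amounts, and the difference favours the non-randomised comparison.

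**Working it through.** The plan states no effect-size value, sample size or power, so there is no figure of its own to reproduce.

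**Inputs**
- Within-arm effect size: mean/Sd of the paired differences (SAP), df = n − 1.
- Between-arm effect size: Cohen's d (SAP, by label), taken as uncorrected with a pooled SD, df = n_ST + n_MST − 2.
- Arm size: not documented. 10, 15 and 20 per arm are assumed, with 6, 30 and 50 to show the range; equal allocation is assumed.
- Normal data. This is the branch in which the SAP uses these ratios, since it tests normality first.

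**Formulas**
- Exact: J(df) = Γ(df/2) / [√(df/2) · Γ((df − 1)/2)].
- Approximate: J(df) ≈ 1 − 3/(4df − 1).
- Expected overstatement = 1/J − 1.

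**Example, 10 per arm**
- Within: J ≈ 1 − 3/(4·9 − 1) = 1 − 3/35 = 0.914; 1/0.914 − 1 = 9.4%.
- Between: J ≈ 1 − 3/(4·18 − 1) = 1 − 3/71 = 0.958; 1/0.958 − 1 = 4.4%.

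**Results (exact J)**

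| n per arm (assumed) | Within-arm overstatement | Between-arm overstatement |
|---|---|---|
| 6 | 18.9% | 8.4% |
| 10 | 9.4% | 4.4% |
| 15 | 5.8% | 2.8% |
| 20 | 4.2% | 2.0% |
| 30 | 2.7% | 1.3% |
| 50 | 1.6% | 0.8% |

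A simulation (400,000 replicates, true effect 0.5) agrees: 9.7% and 4.6% at 10 per arm, 4.2% and 2.1% at 20.

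**Difference between the two measures.** At 10 per arm, 1.094/1.044 = 1.048, so the within-arm figure is inflated by about 5% relative to the between-arm one. At 20 per arm, 1.042/1.020 = 1.022, about 2%.

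**Bias against sampling error, between arms, true d = 0.5.** SE ≈ √(2/n + d²/(4n)).
- 10 per arm: SE = √(0.2 + 0.00625) = 0.454; bias = 0.022; ratio 0.022/0.454 = about 5%.
- 20 per arm: SE = √(0.1 + 0.003125) = 0.321; bias = 0.010; ratio 0.010/0.321 = about 3%.

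**Does the correction cost precision?** No. At 10 per arm and true d = 0.5, the mean squared error is 0.234 for d and 0.214 for Hedges' g. Multiplying by J shrinks the variance as well as removing the bias.

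**The case against.** **The bias is trivial beside the noise.** This stands as a matter of weight. At true d = 0.5 the 5th to 95th percentiles of the observed d run from −0.24 to 1.34 with 10 per arm and from −0.02 to 1.06 with 20. A shift of 0.022 or 0.010 would rarely change an interpretation. It does not make the point wrong, because the bias has a known direction and g is better on both bias and mean squared error.

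**The absence of a between-group correction is inferred.** This also stands. The formula cannot be read, so that half of the point rests on the usual meaning of Cohen's d. The within-group half does not, because its formula is legible.

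**Cohen's d is conventional, and a reader given n can convert it.** True, and reporting d is not an error. But neither document gives n, and the SAP can settle the matter in one sentence.

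**The scope is limited.** Hypothesis tests and p-values do not change. Outcomes handled by rank tests use r = Z/√n, to which this correction does not apply. The documents list no outcomes, so the share affected is unknown.

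**A stronger reading to avoid.** A reader might infer that a later trial sized on these values would be too small. If the *expected* uncorrected d is put into a standard calculation (two-sided 5%, 80% power, true d = 0.5), n per arm = 2(1.960 + 0.842)²/d² gives 63 at the true d, but 58, 60 or 61 at the inflated d from a pilot of 10, 15 or 20 per arm. Actual power would then be 76.8%, 78.2% or 78.9%, against 80.1%. The documents do not support the inference, for three reasons. They describe no such use. A within-arm mean/Sd would not normally size a two-arm comparison, so the larger percentages are not relevant to it. And a bias in expectation is not a statement about one estimate: with 10 or 20 per arm the observed d exceeds a true d of 0.5 with probability 50.6% or 50.4%, so a trial sized on it would be too small about half the time with or without the correction (48.7% and 49.2% for g).

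**Conclusion.** The point holds as a minor reporting matter. For t-test outcomes, the within-group mean/Sd as printed, and the between-group Cohen's d by its usual definition, are biased away from zero on average. If arms hold 10 to 20 participants, the expected overstatement is about 9% falling to 4% within arms and 4% falling to 2% between arms. With 6 per arm it would be about twice the figures at 10, and by 50 per arm it is below 2% in both places.

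These figures assume normal data, equal arms and a pooled SD between groups. The arm size is an assumption, not a fact about this trial. No individual reported value is shown to be too large, and no later trial is shown to be undersized.

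**What to change.** Add one sentence to the SAP's effect-size definitions: report Hedges' g for all t-test outcomes, as

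- within group: mean/Sd × [1 − 3/(4(n − 1) − 1)];
- between group: d × [1 − 3/(4(n_ST + n_MST − 2) − 1)].

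Give n per arm and a confidence interval with each estimate; the interval matters more than the correction, because it shows the sampling error. State that g, not d, is to be used if later planning draws on these estimates. Leave r = Z/√n as it is.

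The cost is one sentence and one multiplication per effect size, plus the intervals. No new data, design change or change to the tests is needed. The only downside for the authors is that the reported effect sizes become slightly less favourable.
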